4.3 Rationale

4.1.1 Rationale for within-subject design

We chose a within-subjects design for several reasons. First, our proposed aims and hypotheses reflect intra-individual change across time. Baseline smoking rate will be established across five days of ad-libitum smoking. Cigarette smoking subsequent to the introduction of IQOS will be compared to each participant's baseline smoking rate (Day 1-5 vs. Day 8-21, see Figure 1). Randomly assigning smokers to continue to smoke their own cigarettes or to switch to IQOS in a between-subjects design is inconsistent with our aims. Second, we do not expect daily cigarette consumption to change in a group of smokers instructed to continue smoking as usual. Third, utilizing a within-subjects design allows us to maximize statistical power and take advantage of the high within-individual correlation of the primary outcome measure so that we can detect differences in smoking behaviors as participants switch to IQOS.

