6. Female participants are advised that participation of pregnant women in this study is prohibited and that they may withdraw at any time.
7. Have height and weight measured.
8. Perform a BrAC assessment to control for alcohol consumption.
9. Participants with a BrAC greater than 0.000 at Intake Visit will be ineligible.

CONFIDENTIAL

This material is the property of the University of Pennsylvania. Do not disclose or use except as authorized in writing by the study sponsor

10. Perform a CO breath assessment and collect self-report smoking behavior over the past 24 hours to control for prior tobacco exposure.
11. Participants with a CO reading less than 10 ppm will be deemed ineligible.
12. Be asked questions about use of marijuana, other tobacco products (besides cigarettes), or vaping of any substance including tobacco/nicotine or other drugs in the past month.
13. Complete a Medical History Form with a member of the research team to review for applicable contraindications, including psychiatric exclusions, previously listed under Inclusion and Exclusion Criteria (section 4.3 and 4.4).
14. Complete a baseline concomitant medication review (if applicable).
15. Complete questionnaires:
16. Demographics
17. Smoking History (e.g., duration, rate, regular and/or menthol)
18. Nicotine Dependence (FTND)
19. Motivation to quit smoking (Contemplation Ladder)
20. Provide instructions to smoke as usual for the first five days of the study protocol (assessment of baseline smoking rate).
21. Be provided with five date-stamped zipped baggies by the research staff.
22. Review a written instruction card for the collection and storage of used cigarette filters with the research staff.
23. Be instructed to engage in overnight smoking abstinence (10-hours) the night of Day 5 in preparation for the Day 6 Visit.
24. Tentatively schedule study visits with a member of the research team.

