7.5 Analytic Plan

Sample size. Hypotheses will be tested with 80% power using a two-sided type-1 error of 5%. The primary outcome is the longitudinal daily count of cigarettes from baseline to the end of the IQOS switch phase. Using simulation methods, with correlated negative-binomial random numbers ($r=0.6$ within subject) and a longitudinal (GEE) negative binomial model, we calculated that we can detect a slope (change per day) of 0.1 cigarettes, or a change of 1.5 cigarettes per day across the two-week switch period. With a lower correlation ($r=0.3$), that detectable effect becomes a slope of 0.15 (change per day) or 2.0 cigarettes per day across the switch period. The secondary outcome is motivation to quit smoking (contemplation ladder), which will also be modeled longitudinally. The contemplation ladder itself has a historical standard deviation of approximately 3.0, and a correlation of 0.3. Our sample of 100 will allow us to detect a change of 0.7 in the contemplation scale in a baseline to end of study comparison.

Data analysis. Prior to analyses, we will: (a) screen the data for data entry errors, (b) check for outliers, and (c) assess the extent and type of missing data, and select the most appropriate method for dealing with the missing data. We will create all summary scores needed for the analysis, and check that the distributional assumptions are met. We will assess for participation biases and differences between participants retained and lost. Analyses will be conducted using Stata software (StataCorp, College Station, Texas).

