The primary outcome is a daily count variable, the number of cigarettes smoked each day. The distribution of cigarettes smoked per day is expected to be over-dispersed (and perhaps zero inflated), because of the study instructions for participants to switch to IQOS heat-sticks for a 14-day period, and the expectation that the majority of participants will have various levels of dual use. The number of IQOS HeatSticks used each day is also a count variable. Participants may have days where they only use IQOS HeatSticks, only smoke cigarettes, and days where they use both. We will accomplish the measurement portion of Aim 1 by summarizing the daily frequencies of cigarettes only, partial switching, and complete switching. Distributional assumptions of all regression methods will be examined in the data set ahead of the analysis to ensure that the best and most representative error model is used. We will examine demographic and other variables for any association with the outcomes or predictors. Those found to be

CONFIDENTIAL

This material is the property of the University of Pennsylvania. Do not disclose or use except as authorized in writing by the study sponsor

associated with outcomes ($p=0.2$) will be included in the model either to correct for confounding or to control error.

The goal of Aim 1 is to evaluate the effects of IQOS use on cigarette smoking behaviors. For the primary analysis, we will analyze the longitudinal counts of cigarettes using mixed models (Gaussian or negative binomial as appropriate). The model will include predictors of time (continuous or discrete), and study phase (baseline versus switch period). We will also include candidate controlling variables (demographic and clinical).

H.1.a. states that IQOS use will decrease the number of cigarettes smoked per day relative to baseline. We do not expect IQOS to replace all cigarettes, and we will measure the use of cigarette smoking only, dual use, and IQOS only use (complete switching). H.1.a. will be tested using the z-score corresponding to the contrast between baseline and switch periods (phase). **H.1.b.** states that the reduction in number of cigarettes smoked per day will be associated with the number of IQOS HeatSticks used. For H.1.b., we will add the daily IQOS use to the model predicting cigarette use, and test using the z-score corresponding to the daily IQOS HeatStick count by phase interaction.

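### The H1a model has no weekend term, so weekend smoking can leak into the phase contrast if start weekdays are uneven; a pre-specified weekend indicator is a cheap safeguard

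*Combined protocol and SAP*

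**What the plan says.** Section 4.1.1 (under 4.3 Rationale) sets the comparison. "Baseline smoking rate will be established across five days of ad-libitum smoking", and later smoking is "compared to each participant's baseline smoking rate (Day 1-5 vs. Day 8-21, see Figure 1").

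Section 7.5 tests H1a by the z-score for the baseline-versus-switch contrast in a mixed model, Gaussian or negative binomial. On its terms it says: "The model will include predictors of time (continuous or discrete), and study phase (baseline versus switch period"). It adds candidate demographic and clinical covariates, and section 7.4.1 adds CO. Section 7.5 also has an open screen of demographic and unlisted further variables, which enter the model if associated with the outcome at p=0.2. None of these names a calendar term. H1b is tested by a different quantity, the HeatStick count by phase interaction.

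The calendar date of every count is available. At Intake participants are to "Be provided with five date-stamped zipped baggies by the research staff" (section 7.2.2), and sections 6.2 and 7.2.4 provide date-stamped bags for the switch phase.

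The only time pattern in smoking that the protocol mentions is variation within the day (section 5.2). It does not mention weekend smoking and does not restrict the weekday of Intake or of Day 1.

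**The concern.** H1a has no concurrent control, so the five baseline days are the only comparator. A five-day window cannot contain the same share of weekend days as a 14-day window. If people smoke differently at weekends, the two phases differ for a reason unrelated to IQOS, and nothing named in the model takes that out. Study-day terms do not stand in for weekday terms, because participants starting on different weekdays reach the same study day on different weekdays.

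At stake is the accuracy of the primary phase effect. Part of a weekly cycle could be reported as an effect of IQOS, or could mask one.

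**Working it through.** **The plan's own benchmark.** Section 7.5 says that, with within-subject correlation 0.6, "we can detect a slope (change per day) of 0.1 cigarettes, or a change of 1.5 cigarettes per day across the two-week switch period". With correlation 0.3, "that detectable effect becomes a slope of 0.15 (change per day) or 2.0 cigarettes per day across the switch period". These figures cannot be reproduced in full, because the mean, the dispersion and the N of the cigarette simulation are not given. The only N in that paragraph belongs to the ladder: "Our sample of 100 will allow us to detect a change of 0.7 in the contemplation scale". A linear approximation for 80% power at two-sided 5% gives

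detectable slope = (1.960 + 0.842) x SD x sqrt((1 - r) / (n x 227.5)),

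where 227.5 is the sum of squared deviations of 14 consecutive days. With n=100 assumed, a slope of 0.1 at r=0.6 implies a daily-count SD of about 8.5, and 0.15 at r=0.3 implies about 9.7. The totals of 1.5 and 2.0, divided by 14 days, imply 9.1 and 9.2. The totals agree with each other (2.0/1.5 = 1.33, against sqrt(0.7/0.4) = 1.32), so 1.5 is a usable yardstick. It is a change across the switch period derived from a slope, not the phase contrast itself.

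**Weekend shares.** Intake is Day 0. Days 8-21 always hold 4 weekend days in 14, or 0.286. Days 1-5 depend on the start. After a Friday Intake they run Saturday to Wednesday, giving 2/5 = 0.400.

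**Leak formulas.** Let D be the weekend-minus-weekday difference in cigarettes/day, taken as additive and equal in both phases.

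- Simple contrast (also what discrete day effects give when averaged within each phase): leak = (switch share - baseline share) x D.
- Linear day plus phase, by least squares on days 1-5 and 8-21: leak = [(switch share - baseline share) - b x 11.5] x D. Here b is the within-phase slope of the weekend indicator on study day, and 11.5 = 14.5 - 3 is the distance between the phase mean days.

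A negative leak with D above zero exaggerates the reduction in smoking, and a positive one hides it.

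| Intake weekday | Weekend days in 1-5 | Simple contrast | b | With linear day |
|---|---|---|---|---|
| Mon | 1 | +0.086 D | 0.0337 | -0.302 D |
| Tue | 2 | -0.114 D | 0.0211 | -0.356 D |
| Wed | 2 | -0.114 D | -0.0042 | -0.066 D |
| Thu | 2 | -0.114 D | -0.0295 | +0.225 D |
| Fri | 2 | -0.114 D | -0.0547 | +0.515 D |
| Sat | 1 | +0.086 D | -0.0084 | +0.183 D |
| Sun | 0 | +0.286 D | 0.0421 | -0.199 D |

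Friday Intake as an example: -0.114 - (-0.0547 x 11.5) = -0.114 + 0.629 = +0.515.

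**Group leak under three start mixes.**

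- Even over seven weekdays: exactly 0 in both models.
- Even Monday-Friday Intake (assumed): simple (0.086 - 4 x 0.114)/5 = -0.074 D; linear (-0.302 - 0.356 - 0.066 + 0.225 + 0.515)/5 = about +0.003 D.
- Even Tuesday-Friday Intake (assumed): simple -0.114 D; linear (-0.356 - 0.066 + 0.225 + 0.515)/4 = about +0.079 D.

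**In cigarettes/day.** D is not in the documents. Taking 1, 2 and 3 as an assumed range:

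| | D=1 | D=2 | D=3 |
|---|---|---|---|
| Even Mon-Fri, simple | -0.07 | -0.15 | -0.22 |
| Even Mon-Fri, linear day | +0.003 | +0.006 | +0.010 |
| All on one weekday, simple (range) | -0.11 to +0.29 | -0.23 to +0.57 | -0.34 to +0.86 |
| All on one weekday, linear day (range) | -0.36 to +0.52 | -0.71 to +1.03 | -1.07 to +1.55 |

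Against 1.5, the even Monday-Friday simple figures are about 5%, 10% and 15%.

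**With a weekend indicator in the model.** A common weekend effect drops out of the phase contrast for any start mix and either time coding. The term is estimable for every start weekday. The variance of the phase contrast is multiplied by 1.00 if starts are even over seven weekdays, and by at most about 1.1 if everyone started on the same weekday.

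**The case against.** The strongest case against acting is that no bias is shown. The mismatch is a property of one participant's calendar and becomes a bias in the group effect only if start weekdays are uneven. The documents do not give their distribution. Weekday-only Intake cannot be presumed either: the visit days in Table 1 (0, 6, 7, 11, 14, 17, 21, 22) cannot all fall on Monday-Friday for any Intake weekday. A Monday Intake puts day 6 on Sunday, and a Friday Intake puts day 22 on Saturday. If visits are moved instead, the windows counted here may move too. D is unsupported by the documents, and the p=0.2 screen could admit a weekend variable. All of this stands, and it is why the point is a safeguard rather than a demonstrated error. It does not remove the gap: the screen commits to no calendar term and would choose one only after the data are seen.

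A reader might also infer three stronger claims, which the documents do not support.

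- *The reduction credited to IQOS is overstated.* That needs D above zero and a negative group leak. The documents establish neither.
- *All Tuesday-Friday starters lean the same way, so a larger sample cannot help.* This is true of the simple contrast only. With the linear day term that section 7.5 allows, the leak runs from -0.356 D (Tuesday) to +0.515 D (Friday), and their even mix has the opposite sign.
- *H1b is biased in the same way.* H1b tests the HeatStick by phase interaction, which the baseline weekend-share argument does not reach.

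**Conclusion.** The point holds as a gap in specification. The H1a model omits a weekend or day-of-week term, no participant's baseline can match the weekend share of the switch phase, and start weekdays are neither fixed nor balanced. A leak into the phase contrast is therefore possible, but its direction and size are unknown. Both depend on D, on the mix of start weekdays, and on whether time is coded as continuous or discrete, which section 7.5 leaves open.

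Under the mixes that spread starts over several weekdays, the leak is zero to about 0.11 x D in absolute value, which is probably modest against 1.5 cigarettes/day. Only strong clustering on one start weekday together with a large D would make it comparable to 1.5, and the documents show no such clustering. The figures assume an additive weekend effect common to both phases, a Gaussian least-squares approximation, and complete daily counts. Under a negative binomial model the same argument applies on the log scale, with different numbers.

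**What to change.** In section 7.5, pre-specify a weekend indicator (Saturday or Sunday, from the date on the bag) as a fixed covariate in the H1a model, kept whatever the p=0.2 screen shows. Report the phase effect at a common 5:2 weekday:weekend mix in both phases. This matters mainly for a negative binomial model, where the absolute difference depends on the mix. Tabulating the weekday of Day 1 would let readers judge how uneven the starts were.

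The cost is one degree of freedom and a small loss of precision: none with even starts, and at most about 10% in variance if all starts fell on one weekday. No new data are needed. The indicator removes only a weekend effect common to both phases. A weekend effect that changes once IQOS is supplied would need a separate sensitivity analysis.

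The same term may be carried into the H1b model as a precaution, since weekends could move same-day cigarettes and HeatSticks together. That is a separate mechanism, and the magnitudes above do not apply to it.

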8.1 Potential Study Risks

The potential risks to participants, their likelihood and seriousness, and strategies to mitigate risks are described below. Participants can choose, as an alternative, to not enroll in this study. Overall, there is minimal risk for serious adverse reactions as a consequence of enrolling in this study. Adverse reactions/AEs will be collected, assessed, and reported as per the study protocol (see section 8: Safety and Adverse Events), federal law, and University of Pennsylvania regulations.

Reproductive Risks: Smoking can cause serious harm to unborn children or children who are breast-feeding. Female participants are asked to use a medically accepted method of birth control (such as IUD, birth control pills, condoms, etc.) while participating in the study. Further, female participants, and those assigned as female at birth, will be asked to administer a simple, one-step hCG pregnancy test and informed that if they are (or believe they may be) pregnant that they will not be eligible to participate in the research study. If a female participant becomes pregnant over the course of the trial, they will be immediately withdrawn. It will also be recommended that the participant seek consult from an obstetrician or maternal-fetal specialist about the dangers of smoking while pregnant.

CONFIDENTIAL

This material is the property of the University of Pennsylvania. Do not disclose or use except as authorized in writing by the study sponsor

Withdrawal Symptoms: Participants may experience uncomfortable withdrawal symptoms during their overnight smoking abstinence. In preparation for the overnight abstinence, participants will receive tips for remaining abstinent (e.g., coping with withdrawal and craving, smoking triggers, coping with stress). Participants will also be reminded that these symptoms will be short-lived and that they will be able to self administer nicotine in the laboratory the following morning.

Assessments: Some participants may experience some emotional distress during the assessments due to learning their carbon monoxide levels or seeing how many cigarettes and/or HeatSticks they smoke. These events happen very rarely and in almost all cases are short-lived and of low intensity. If a participant does exhibit a high level of emotional distress, however, they will be offered contact information for mental health services in the area.

Cigarette Smoking and IQOS use: Although cigarette smoking is associated with many diseases, we do not believe the risk is beyond every day risk as all participants must be current cigarette smokers to be eligible. We will inform participants that cigarette smoking has been shown to cause diseases such as emphysema and cancer. There will be a phase of the study where participants will be instructed to switch completely to IQOS. If participants don't completely switch from smoking cigarettes to using IQOS, their risks from smoking will remain the same.

Important safety information regarding IQOS: IQOS works exclusively with HeatSticks. Never use IQOS with a cigarette or any other tobacco sticks or accessories. Do not remove a tobacco stick (HeatStick) while in use. Tobacco sticks (HeatSticks) are single use only and should never be reused. Tobacco sticks (HeatSticks) should never be lit with a match, lighter, or any other flame source. **Keep tobacco sticks out of reach of children and pets.** If tobacco sticks are swallowed, seek medical attention immediately due to risk of nicotine ingestion. **Store your tobacco sticks in a cool, dry place.** Do not expose product to high humidity conditions or direct sunlight. Do not use IQOS during hot conditions or in periods of high humidity. **Pay attention to signs that your battery may be leaking.** The IQOS Holder and Pocket Charger are powered with sealed Lithium-ion batteries. Under normal conditions of use, the battery is sealed. If you notice fluid leaking from the battery, follow these precautions, discontinue using the product immediately and contact *[name]* at [contact], or *[name]* at [contact]. In case of contact with skin, wash hands and do not touch eyes. In case of contact with eyes, immediately flush with running water for at least 15 minutes and seek medical attention. If fluid is inhaled, get fresh air and seek medical attention. If you swallow fluid, seek medical attention immediately. Do not induce vomiting or ingest food or drink. **Stop using IQOS and seek medical attention immediately if you experience any symptoms that may indicate a serious allergic reaction:** swelling of the face, lips, tongue, gums, throat, or body; difficulty breathing, or wheezing.

Email Communications: In this research study participants may prefer to receive appointment reminders via email or submit questions related participation via email. Email is not a secure means of communication. Email messages travel across the Internet passing through multiple computers before reaching their final destination. It is not possible to know whether an email a participant sends will be viewed along the way. Additionally, if sent messages are not deleted, an email provider may have an archive of everything that is sent. If someone gets access to an email account (for example, a participant's family member), they could see archived messages. There are many other ways in which emails are not secure—these are only selected examples. To manage this risk the informed consent form will include specific language to educate research participants on the privacy risks involved in email communications. Participants will also be

CONFIDENTIAL

This material is the property of the University of Pennsylvania. Do not disclose or use except as authorized in writing by the study sponsor

explicitly instructed to only use email communications for routine matters and never for personal or confidential messages or questions.

Confidentiality and Loss of Privacy: See section 9.6.1 and 9.6.2 for methods in which Confidentiality and Subject Privacy/Protected Health Information will be secured and maintained.

8.2 Potential Study Benefits

Cigarette smokers may benefit from participation by knowing that they are contributing to research that can help determine if (1) IQOS is an acceptable alternative to combustible cigarette smoking among smokers like themselves, (2) IQOS fully replace cigarettes, and (3) IQOS lessens motivation to quit smoking. The proposed study is expected to yield new knowledge regarding the subjective, objective, and behavioral impact of IQOS on cigarette smoking behaviors. The findings will inform public health interventions and regulatory actions to educate and protect smokers if they choose to use IQOS.

8.3 Risk/Benefit Assessment

The potential benefits of this study outweigh the potential risks. There is only a minimal risk of experiencing study-related AEs or SAEs by enrolling in this trial. The findings from this study will inform public health interventions and regulatory actions to educate and protect smokers if they choose to use IQOS.

8.3.1 Adequacy of Protection against Risks

Informed Consent. Informed consent/HIPPA forms will be signed electronically on REDCap or at the Intake Visit before any research activities are completed. Trained staff will provide a study overview, including the risk and benefits of being in the study. Staff will respond to all questions and inform potential participants that participation is voluntary. Preliminarily eligible smokers adults will be asked to provide informed consent for participation. After receiving informed consent, participants will provide a urine sample to assess drug use and/or pregnancy, which are exclusions for participation. Participants will receive a copy of their signed consent form.

Oversight and Monitoring. The Institutional Review Board at the University of Pennsylvania will monitor the protection of human subjects and the safe and secure collection and storage of data. This committee will assess the study before initiation and then annually at the time of Continuing Review. The IRB will ensure the scientific, technical, and statistical soundness of the research and guarantee that methods for the ethical and safe treatment of human subjects are in place.

Participant Safety. Eligibility criteria for this study will exclude any individual who would be at risk of adverse effects from participation in this study. Participant safety begins with the PI's thorough training and ongoing supervision of the project staff and study procedures. Weekly meetings will ensure an understanding and adherence to the study goals and data collection and management procedures. Personnel training by the PI will be considered to be of the highest priority and will be addressed prior to the start of the study and on an ongoing basis. Training will help ensure that all processes and procedures for data collection and management are correctly applied and utilized. Specifically, but not exclusively, this training will ensure that research personnel understand the study's goals and objectives, data collection process, confidentiality, participant safety, all case report forms (CRFs), the manual of procedures (MOP), database software and the data management system (DMS), and all applicable standard operating procedures (SOPs) to attest that the study is conducted in a proper manner. Training will span study recruitment approaches, screening, assessment, follow-up of rescheduled participants, data entry and storage, and tracking study incentives.

CONFIDENTIAL

This material is the property of the University of Pennsylvania. Do not disclose or use except as authorized in writing by the study sponsor

Data Management. The CIRNA Data Management Core will be responsible for the data management system, the operational facets of this study, quality assurance, and data storage.

Data Collection, Processing, and Management. All data collection, processing, and management procedures will be standardized in a detailed Manual of Procedures (MOP). Hard-copy surveys will serve as source documents. All data are entered into a database located upon the secure server with dedicated uninterrupted power at the CIRNA. All indicated data entry and processing operations will be performed using Data Management System (DMS) software. Study personnel will access the menu driven DMS software to perform specific operations. For example, the DMS functionality will include subject tracking, data entry, data validation, and query tracking, standard reports, and tracking of all major study milestones (e.g., assessment and visit disposition), and the counterbalanced sequence of the order of IQOS flavors on the day 6 laboratory visit.

Quality and Data Safety Assurance Practices. The PI will conduct training to ensure that all processes and procedures for data collection and procedures for data collection, processing, and storage are correctly applied and utilized. Confidential participant information will be collected and entered into the database. When this information exists on paper (e.g., updated contact information, alternative contact information) it will always be filed under lock and key. Upon entry of this data into the database, an auto-study ID will be generated. The auto-study ID will then generate and be linked to a participant ID in a separate table. Thus, contact information will never exist in the same DMS table as a participant ID. No one can gain access to an individual database unless they have been explicitly granted a user ID and password. The Center's database server and individual study databases have never been compromised as a result of the extremely rigorous and secure network firewall technologies. The secure servers are located in a specially designed, highly secured facility with dedicated uninterrupted power supply. Access to this server facility is strictly limited.

Adverse Event Reporting. In accordance with NIH and IRB guidelines, this protocol will employ the following mechanisms for adverse event reporting: (1) alert the IRB of any and all reports of serious adverse events; (2) inform all members of the study team of any and all reports of serious adverse events; (3) notify the NIH of any actions taken by IRB with regard to data safety monitoring.

9 Safety and Adverse Events

